3.3.3 Women of Childbearing Potential

A Women of childbearing potential (WOCBP) is defined as any female who has experienced menarche and who has not undergone surgical sterilization (hysterectomy or bilateral oophorectomy) and is not postmenopausal. Menopause is defined as 12 months of amenorrhea in a woman over age 45 years in the absence of other biological or physiological causes. In addition, females under the age of 55 years must have a serum follicle stimulating hormone, (FSH) level > 40mIU/mL to confirm menopause.

*Females treated with hormone replacement therapy, (HRT) are likely to have artificially suppressed FSH levels and may require a washout period in order to obtain a physiologic FSH level. The duration of the washout period is a function of the type of HRT used. The duration of the washout period below are suggested guidelines and the investigators should use their judgment in checking serum FSH levels. If the serum FSH level is >40 mIU/ml at any time during the washout period, the woman can be considered postmenopausal:

- 1 week minimum for vaginal hormonal products (rings, creams, gels)
- 4 week minimum for transdermal products
- 8 week minimum for oral products.

Other parenteral products may require washout periods as long as 6 months.

[REDACTED]

[Redacted]

[Redacted]

[Redacted]

[Redacted]

[Redacted]

[Redacted]

[Redacted]

All subjects who discontinue study drug should comply with protocol specified follow-up procedures as outlined in [Section 5](#). The only exception to this requirement is when a subject withdraws consent for all study procedures including post-treatment study follow-up or loses the ability to consent freely (ie, is imprisoned or involuntarily incarcerated for the treatment of either a psychiatric or physical illness).

If study drug is discontinued prior to the subject's completion of the study, the reason for the discontinuation must be documented in the subject's medical records and entered on the appropriate case report form (CRF) page.

3.6 Post Study Drug Study Follow up

In this study, clinical benefit rate is the primary endpoint of the study. Post study follow-up is of critical importance and is essential to preserving subject safety and the integrity of the study. Subjects who discontinue study drug must continue to be followed for collection of outcome and/or survival follow-up data as required and in line with [Section 5](#) until death or the conclusion of the study.

BMS may request that survival data be collected on all treated subjects outside of the protocol defined window ([Table 5.1-4](#)). At the time of this request, each subject will be contacted to determine their survival status unless the subject has withdrawn consent for all contacts or is lost to follow-up.

3.6.1 Withdrawal of Consent

Subjects who request to discontinue study drug will remain in the study and must continue to be followed for protocol specified follow-up procedures. The only exception to this is when a subject specifically withdraws consent for any further contact with him/her or persons previously authorized by subject to provide this information. Subjects should notify the investigator of the decision to withdraw consent from future follow-up **in writing**, whenever possible. The withdrawal of consent should be explained in detail in the medical records by the investigator, as to whether the withdrawal is from further treatment with study drug only or also from study procedures and/or post treatment study follow-up, and entered on the appropriate CRF page. In the event that vital status (whether the subject is alive or dead) is being measured, publicly available information should be used to determine vital status only as appropriately directed in accordance with local law.

3.6.2 Lost to Follow-Up

All reasonable efforts must be made to locate subjects to determine and report their ongoing status. This includes follow-up with persons authorized by the subject as noted above. Lost to follow-up is defined by the inability to reach the subject after a minimum of three documented phone calls, faxes, or emails as well as lack of response by subject to one registered mail letter. All attempts should be documented in the subject's medical records. If it is determined that the subject has died, the site will use permissible local methods to obtain the date and cause of death.

If investigator's use of third-party representative to assist in the follow-up portion of the study has been included in the subject's informed consent, then the investigator may use a Sponsor-retained

third-party representative to assist site staff with obtaining subject's contact information or other public vital status data necessary to complete the follow-up portion of the study. The site staff and representative will consult publicly available sources, such as public health registries and databases, in order to obtain updated contact information. If after all attempts, the subject remains lost to follow-up, then the last known alive date as determined by the investigator should be reported and documented in the subject's medical records.

4 STUDY DRUG

Study drug includes both Investigational [Medicinal] Product (IP/IMP) and Non-investigational [Medicinal] Product (Non-IP/Non-IMP) and can consist of the following (Table 4-1):

- All products, active or placebo, being tested or used as a comparator in a clinical trial.
- Study required premedication, and
- Other drugs administered as part of the study that are critical to claims of efficacy (eg, background therapy, rescue medications)
- Diagnostic agents: (such as glucose for glucose challenge) given as part of the protocol requirements must also be included in the dosing data collection.

Table 4-1: Study Drugs for CA209204

Product Description / Class and Dosage Form	Potency	IP/Non-IMP	Blinded or Open Label	Packaging/ Appearance	Storage Conditions (per label)
Nivolumab Solution for Injection	100 mg (10 mg/mL)	IP	Open-label	Clear to opalescent colorless to pale yellow liquid. May contain particles	2 to 8° C. Protect from light, freezing and shaking.
Ipilimumab Solution for Injection	200 mg (5 mg/mL)	IP	Open-label	Clear, colorless to pale yellow liquid. May contain particles	2 to 8° C. Protect from light and freezing.

Premedications or medications used to treat infusion-related reactions should be sourced by the investigative sites if available and permitted by local regulations.

4.1 Investigational Product

An investigational product, also known as investigational medicinal product in some regions, is defined a pharmaceutical form of an active substance or placebo being tested or used as a reference in a clinical study, including products already with a marketing authorization but used or assembled (formulated or packaged) differently than the authorized form, or used for an unauthorized indication, or when used to gain further information about the authorized form.

The investigational product should be stored in a secure area according to local regulations. It is the responsibility of the investigator to ensure that investigational product is only dispensed to study subjects. The investigational product must be dispensed only from official study sites by authorized personnel according to local regulations.

In this protocol, investigational products are nivolumab and ipilimumab.

4.2 Non-investigational Product

Other medications used as support or escape medication for preventative, diagnostic, or therapeutic reasons, as components of the standard of care for a given diagnosis, may be considered as non-investigational products.

4.3 Storage and Dispensing

The product storage manager should ensure that the study drug is stored in accordance with the environmental conditions (temperature, light, and humidity) as determined by BMS. If concerns regarding the quality or appearance of the study drug arise, the study drug should not be dispensed and contact BMS immediately.

Investigational product documentation (whether supplied by BMS or not) must be maintained that includes all processes required to ensure drug is accurately administered. This includes documentation of drug storage, administration and, as applicable, storage temperatures, reconstitution, and use of required processes (eg, required diluents, administration sets).

Infusion-related supplies (eg IV bags, in-line filters, 0.9% NaCl solution) will not be supplied by the sponsor and should be purchased locally if permitted by local regulations.

For non-investigational product, if marketed product is utilized, it should be stored in accordance with the package insert, summary of product characteristics (SmPC), or similar.

Please refer to the current version of the nivolumab and ipilimumab IBs and/or pharmacy reference sheets for complete storage, handling, dispensing, and infusion information for BMS-936558 (nivolumab) and BMS-734016 (ipilimumab).

Nivolumab

Nivolumab vials must be stored at a temperature of 2° C to 8° C and should be protected from light, freezing, and shaking. If stored in a glass front refrigerator, vials should be stored in the carton. Recommended safety measures for preparation and handling of nivolumab include laboratory coats and gloves.

For details on prepared drug storage and use time of nivolumab under room temperature/light and refrigeration, please refer to the nivolumab IB section for “Recommended Storage and Use Conditions” and/or pharmacy reference sheets. Care must be taken to assure sterility of the prepared solution as the product does not contain any anti-microbial preservative or bacteriostatic agent. No incompatibilities between nivolumab and polyolefin bags have been observed.

Nivolumab is to be administered as a 60-minute IV infusion \pm 10 minutes using a volumetric pump with a 0.2/0.22 micron in-line filter at the protocol-specified dose. The drug can be diluted with 0.9% normal saline for delivery but the total drug concentration of the solution cannot be below 0.35 mg/ml. It is not to be administered as an IV push or bolus injection. At the end of the infusion, flush the line with a sufficient quantity of normal saline.

Ipilimumab

Ipilimumab injection can be used for IV administration without dilution after transferring to a PVC (polyvinyl chloride), non-PVC/non-DEHP (di-(2-ethylhexyl)phthalate) or glass containers and is stable for 24 hours at 2-8°C or room temperature/room light (RT/RL). For ipilimumab storage instructions, refer to ipilimumab IB and/or pharmacy reference sheets. Recommended safety measures for preparation and handling include protective clothing, gloves, and safety cabinets.

Ipilimumab is to be administered as a 90-minute IV infusion \pm 10 minutes, using a volumetric pump with a 0.2 to 1.2 micron in-line filter at the protocol-specified dose. The drug can be diluted with 0.9% normal saline or 5% Dextrose Injection to concentrations between 1 mg/mL and 4 mg/mL. It is not to be administered as an IV push or bolus injection. Care must be taken to assure sterility of the prepared solutions, since the drug product does not contain any antimicrobial preservatives or bacteriostatic agents.

When both study drugs are to be administered on the same day, separate infusion bags and filters must be used for each infusion. Nivolumab is to be administered first. The nivolumab infusion must be promptly followed by a saline flush to clear the line of nivolumab before starting the ipilimumab infusion.

4.4 Method of Assigning Subject Identification

CA209204 study is an open-label study. After the subject’s initial eligibility is established and informed consent has been obtained, the subject must be enrolled into the study by calling an interactive voice response system (IVRS) to obtain the subject number. Every subject that signs the informed consent form must be assigned a subject number in IVRS. Specific instructions for using IVRS will be provided to the investigational site in a separate document. The investigator or designee will register the subject for enrollment by following the enrollment procedures established by BMS. The following information is required for enrollment:

- Date that informed consent was obtained
- Date of birth
- Gender at birth

4.5 Selection and Timing of Dose for Each Subject.

All enrolled subjects will be treated in an open-label fashion as described below:

- Nivolumab administered IV over 60 minutes \pm 10 minutes at 1 mg/kg combined with ipilimumab administered IV over 90 minutes \pm 10 minutes at 3 mg/kg every 3 weeks for a total of 4 doses of the combination therapy followed by nivolumab administered IV over 60 minutes \pm 10 minutes at 3mg/kg every 2 weeks for a maximum of 24 months or until progression or unacceptable toxicity.

Dosing schedule is detailed in [Table 4.5-1](#) and [Table 4.5-2](#) .

Table 4.5-1: CA209204: Dosing Schedule for Cycle 1 and Cycle 2

1 Cycle = 6 weeks						
	Day 1 Week 1	Day 1 Week 2	Day 1 Week 3	Day 1 Week 4	Day 1 Week 5	Day 1 Week 6
All Enrolled Subjects Combination Treatment (Nivolumab 1mg/kg + Ipilimumab 3 mg/kg)	1 mg/kg Nivolumab + 3 mg/kg Ipilimumab			1 mg/kg Nivolumab + 3 mg/kg Ipilimumab		

Table 4.5-2: CA209204 Dosing Schedule Cycle 3 and Beyond

Subjects may continue to receive treatment for a maximum of 24 months from the Date of the First Treatment with Nivolumab +Ipilimumab.

1 Cycle = 6 weeks

	Day 1 Week 1	Day 1 Week 2	Day 1 Week 3	Day 1 Week 4	Day 1 Week 5	Day 1 Week 6
All Enrolled Subjects Nivolumab monotherapy	3 mg/kg Nivolumab		3 mg/kg Nivolumab		3 mg/kg Nivolumab	

4.5.1 Antiemetic Premedications

Antiemetic premedications should not be routinely administered prior to dosing of drugs. See [Section 4.5.6](#) for premedication recommendations following either a nivolumab- or an ipilimumab-related infusion reaction.

4.5.2 Dose Delay Criteria

Dose delay criteria apply for all drug-related adverse events (regardless of whether or not the event is attributed to nivolumab, ipilimumab, or both). All study drugs must be delayed until treatment can resume. See [Section 4.5.4](#).

Ipilimumab and / or nivolumab administration should be delayed for the following:

- Any Grade ≥ 2 non-skin, drug-related adverse event, with the following exceptions:
 - Grade 2 drug-related fatigue or laboratory abnormalities do not require a treatment delay
- Any Grade 3 skin, drug-related adverse event
- Any Grade 3 drug-related laboratory abnormality, with the following exceptions for lymphopenia, AST, ALT, or total bilirubin or asymptomatic amylase or lipase:
 - Grade 3 lymphopenia does not require dose delay
 - If a subject has a baseline AST, ALT, or total bilirubin that is within normal limits, delay dosing for drug-related Grade ≥ 2 toxicity
 - If a subject has baseline AST, ALT, or total bilirubin within the Grade 1 toxicity range, delay dosing for drug-related Grade ≥ 3 toxicity
 - Any Grade ≥ 3 drug-related amylase or lipase abnormality that is not associated with symptoms or clinical manifestations of pancreatitis does not require dose delay. The BMS Medical Monitor should be consulted for such Grade ≥ 3 amylase or lipase abnormalities.
- Any adverse event, laboratory abnormality, or intercurrent illness which, in the judgment of the investigator, warrants delaying the dose of study medication.

Subjects who require delay of ipilimumab or nivolumab should be re-evaluated weekly or more frequently if clinically indicated and resume ipilimumab or nivolumab dosing when re-treatment criteria are met.

Tumor assessments should continue as per protocol even if dosing is delayed.

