4.5.2.2 Resumption of Treatment after Dose Delay

If there is a delay in treatment due to AEs associated with study medication, when the patient resumes treatment, he/she will receive the next dose, rather than the missed dose. If the dose delay occurs during the combination treatment (induction), the patient will receive less than 4 doses of the combination treatment.

If there is a delay due to SRT or AEs not associated with study medication, when the patient resumes treatment, he/she will receive the missed dose. If the dose delay occurs during the combination treatment (induction), the patient has the opportunity to receive all four doses of the combination treatment.

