4.5.4 Criteria to Resume Treatment

Subjects may resume treatment with study drug when the drug-related AE(s) resolve to Grade \leq 1 or baseline value, with the following exceptions:

- Subjects may resume treatment in the presence of Grade 2 fatigue
- Subjects who have not experienced a Grade 3 drug-related skin AE may resume treatment in the presence of Grade 2 skin toxicity

- Subjects with baseline Grade 1 AST/ALT or total bilirubin who require dose delays for reasons other than a 2-grade shift in AST/ALT or total bilirubin may resume treatment in the presence of Grade 2 AST/ALT OR total bilirubin
- Subjects with combined Grade 2 AST/ALT AND total bilirubin values meeting discontinuation parameters (Section 4.5.5) should have treatment permanently discontinued.
- Drug-related pulmonary toxicity, diarrhea, or colitis must have resolved to baseline before treatment is resumed. Subjects with persistent Grade 1 pneumonitis after completion of a steroid taper over at least 1 month may be eligible for retreatment if discussed with and approved by the BMS Medical Monitor.
- Drug-related endocrinopathies adequately controlled with only physiologic hormone replacement may resume treatment after consultation with the BMS Medical Monitor

Dose delay of treatment that results in treatment interruption of > 6 weeks requires treatment discontinuation, with exceptions as noted in [Section 4.5.2.1](#) and Section 4.5.5

There will be no dose reductions for study medications.

If the criteria to resume treatment are met, the subject should restart treatment at the next scheduled time point per protocol. However, if the treatment is delayed past the next scheduled time point per protocol, the next scheduled time point will be delayed until dosing resumes.

- If treatment is delayed > 6 weeks, the subject must be permanently discontinued from study therapy, except as specified in Section 4.5.2.1 and Section 4.5.5.

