4.5.5 Discontinuation of Study Drug

Treatment should be permanently discontinued for the following:

- Any Grade 2 drug-related uveitis or eye pain or blurred vision that does not respond to topical therapy and does not improve to Grade 1 severity within the re-treatment period OR requires systemic treatment
- Any Grade 3 non-skin, drug-related adverse event lasting > 7 days, with the following exceptions for laboratory abnormalities, drug-related uveitis, pneumonitis, bronchospasm, hypersensitivity reactions, infusion reactions, and endocrinopathies:
 - Grade 3 drug-related uveitis, pneumonitis, bronchospasm, hypersensitivity reaction, or infusion reaction of any duration requires discontinuation
 - Grade 3 drug-related endocrinopathies adequately controlled with only physiologic hormone replacement do not require discontinuation
 - Grade 3 drug-related laboratory abnormalities do not require treatment discontinuation except:
 - ◆ Grade 3 drug-related thrombocytopenia > 7 days or associated with bleeding requires discontinuation
- Any drug-related liver function test (LFT) abnormality that meets the following criteria require discontinuation:
 - AST or ALT > 8 x ULN

- Total bilirubin > 5 x ULN
- Concurrent AST or ALT > 3 x ULN and total bilirubin > 2 x ULN
- Any Grade 4 drug-related adverse event or laboratory abnormality, except for the following events which do not require discontinuation:
 - Grade 4 neutropenia ≤ 7 days
 - Grade 4 lymphopenia or leukopenia
 - Isolated Grade 4 amylase or lipase abnormalities that are not associated with symptoms or clinical manifestations of pancreatitis. The BMS Medical Monitor should be consulted for Grade 4 amylase or lipase abnormalities.
 - Isolated Grade 4 electrolyte imbalances/abnormalities that are not associated with clinical sequelae and are corrected with supplementation/appropriate management within 72 hours of their onset
- Any event that leads to delay in dosing lasting > 6 weeks from the previous dose requires discontinuation, with the following exceptions:

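### Protocol 4.5.2 both exempts and requires a dose delay for a drug-related Grade 2 AST, ALT or bilirubin value when baseline was normal

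*Protocol*

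**What the plan says.** Protocol 4.5.2 lists the situations in which nivolumab and/or ipilimumab should be delayed. Three items bear on laboratory values.

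- The first trigger is any Grade 2 or higher "non-skin, drug-related adverse event, with the following exceptions". Its only exception is that "Grade 2 drug-related fatigue or laboratory abnormalities do not require a treatment delay".
- The third trigger is a drug-related laboratory abnormality of Grade 3. Its exceptions cover lymphopenia, liver tests, and amylase or lipase without symptoms. Two of these sub-items form the liver rule:
  - "If a subject has a baseline AST, ALT, or total bilirubin that is within normal limits, delay dosing for drug-related" toxicity of Grade 2 or higher;
  - "If a subject has baseline AST, ALT, or total bilirubin within the Grade 1 toxicity range, delay dosing for drug-related" toxicity of Grade 3 or higher.
- The last trigger leaves room for judgment: "Any adverse event, laboratory abnormality, or intercurrent illness which, in the judgment of the investigator, warrants delaying the dose of study medication".

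Three nearby sections matter. In 4.5.2.2, after a delay for a drug-related event the subject moves on to the next dose, and "If the dose delay occurs during the combination treatment (induction), the patient will receive less than 4 doses of the combination treatment". In 4.5.4, subjects with a Grade 1 liver baseline whose delay had some cause other than a two-grade shift in these tests "may resume treatment in the presence of Grade 2 AST/ALT OR total bilirubin". In 4.5.5, one of the liver criteria for permanent discontinuation is "Concurrent AST or ALT > 3 x ULN and total bilirubin > 2 x ULN".

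**The concern.** A drug-related Grade 2 ALT is a laboratory abnormality, so the exemption covers it as worded. If that subject's baseline ALT was normal, the liver rule covers it too and says the opposite. There is no cross-reference and no statement of precedence.

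The layout adds to the difficulty. The Grade 2 liver instruction sits as an exception under a trigger headed Grade 3. Someone holding a Grade 2 result meets the exemption first and has little reason to look under the Grade 3 item. The neighbouring exceptions for lymphopenia and for amylase or lipase remove a delay, whereas the normal-baseline liver line adds one at a lower grade.

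The rule is in routine use. Table 5.1-2 has liver tests drawn within 72 hours before each combination dose, and 5.3.7 requires safety laboratory results to be reviewed before dosing. Section 3.1 gives liver tests as one example of the regimen's most frequent severe drug-related events. What is at stake is whether the next dose is given and, in induction, whether a combination dose is lost.

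**Working it through.** The plan has no figure to reproduce here. The check is to read the lines literally for every relevant case and then follow the dosing consequence.

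**Inputs.** From 4.5.2: the first trigger with its Grade 2 laboratory exemption, the Grade 3 laboratory trigger, and the two liver lines. From 4.5: four combination doses, each of nivolumab 1 mg/kg plus ipilimumab 3 mg/kg. From 4.5.2.2: a dose delayed for a drug-related event is not made up.

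**Step 1. Where the lines disagree.** For a drug-related AST, ALT or bilirubin value:

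| Baseline | On-study grade | General lines | Liver rule | Conflict |
|---|---|---|---|---|
| Normal | 1 | not triggered | not triggered | no |
| Normal | 2 | no delay required | delay | **yes** |
| Normal | 3 | delay | delay | no |
| Normal | 4 | delay | delay | no |
| Grade 1 | 1 | not triggered | not triggered | no |
| Grade 1 | 2 | no delay required | not triggered | no |
| Grade 1 | 3 | delay | delay | no |
| Grade 1 | 4 | delay | delay | no |

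One of the eight combinations conflicts. Restricted to Grades 2 and 3, it is one of four.

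**Step 2. Which line is meant.** The liver rule names the tests and is a direct instruction. Its two thresholds are both two-grade shifts (normal to Grade 2, Grade 1 to Grade 3), which is the idea 4.5.4 uses. Section 4.5.4 also allows resumption at a Grade 2 liver value only for a Grade 1 baseline. Both points indicate that the liver rule should govern.

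**Step 3. Consequence in induction, for a subject with no other delay.**

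- Dose given under the exemption: 4 doses. Ipilimumab 4 × 3 = 12 mg/kg; nivolumab 4 × 1 = 4 mg/kg.
- Dose delayed under the liver rule: fewer than 4, so at most 3. Ipilimumab at most 3 × 3 = 9 mg/kg; nivolumab at most 3 × 1 = 3 mg/kg.
- Difference: at least 1/4 = 25% fewer combination doses.

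**Step 4. After the fix.** If the liver rule alone governs these three tests, the conflicting row disappears and the count is 0 of 8. This requires a pointer to the liver rule as well as an exclusion. With a bare exclusion, a Grade 2 value on a Grade 1 baseline would fall back under the first trigger and call for a delay that the liver rule does not ask for.

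**The case against.** The strongest reply is structural. Section 4.5.2 is a list of separate triggers, and the Grade 2 line is indented under the first. On that reading it switches off the first trigger only and leaves the third, with its liver rule, in force. The normal-baseline Grade 2 case is then exempt under one trigger and delayed under another, with no contradiction.

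That reading does not fit the rest of the list. The first trigger catches any non-skin drug-related event of Grade 2 or higher and exempts laboratory abnormalities only at Grade 2. If each exception worked only within its own item, Grade 3 lymphopenia and symptom-free Grade 3 lipase would be excused under the third trigger but still delayed under the first, and their exceptions would do nothing. The exceptions therefore have to work across the list, and then the Grade 2 exemption does meet the liver rule head on.

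Other parts of the reply stand. The intended rule can be worked out, with help from 4.5.4. A careful site would hold the dose. Losing a combination dose is the ordinary effect of 4.5.2.2 on any drug-related delay; the gap between four and at most three doses reflects this conflict only if a site follows the exemption instead. Giving the dose does not secure four either, since later toxicity may intervene. The judgment item in 4.5.2 and the liver criteria in 4.5.5 limit harm. This is a wording fault, and no threshold is in dispute.

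**Conclusion.** The point holds, at low severity. As written, 4.5.2 gives opposite instructions for one case: normal baseline with a drug-related Grade 2 AST, ALT or total bilirubin. For a subject in induction with no other delay, the two lines separate four combination doses from at most three.

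This rests on reading the exemption as worded and on the exceptions applying across the list, which the lymphopenia and lipase exceptions need in order to have any effect. The documents give no rate for Grade 2 liver values after a normal baseline, and none for sites following the exemption, so no number of affected subjects can be given. The definition of intracranial CBR, the sample size of 110 and the planned analysis do not change.

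**What to change.** Qualify the Grade 2 exemption in 4.5.2 with words such as: *except AST, ALT or total bilirubin, for which the baseline-specific rules below apply instead*. Then lift the two liver lines out from under the Grade 3 item and list them as their own trigger, so that a Grade 2 instruction no longer sits under a Grade 3 heading. The qualifying words are the essential part; moving the lines is for clarity.

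Keep both thresholds. Sections 4.5.2.2, 4.5.4 and 4.5.5 need no change. The cost is one added phrase and two relocated lines, with no new assessments and no effect on the analysis. Administrative Letter 04 already served to clarify dosing in the study design figure, so there is a precedent for a short clarification to sites.
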